## 5.2 Investigational Study Drug Combination (THRIL)

### **Starting with Cycle 1:**

#### **A cycle is 28 days:**

Thalidomide 50 mg every ODD day, days 1-28 every 28 days

Lenalidomide every EVEN day, days 1-28 every 28 days at the dose indicated above and with possible dose escalation as described in 5.1.

Rituximab 375 mg/m^2 IV on days 1, 8, 15 and 22 (+/- 2 days) starting with Cycle 1 and then again on the same weekly x 4 schedule every 6th cycle through Cycle 19 (Cycles 7, 13, and 19).

Responses will be assessed at monthly intervals using the response criteria outlined by the IWCLL update of the 1996 NCI-Working Group criteria. Patients will remain on treatment until they demonstrate disease progression or unacceptable toxicity. It will be important for the investigator to differentiate disease progression from tumor flare. While no strict criteria can be established for this distinction, rapid changes in clinical status that occur within four weeks of a dose escalation are likely to be tumor flares and should be treated as such.

Tumor flare has been described with both thalidomide and lenalidomide treatment. Therefore, patients should be monitor closely for signs and symptoms of tumor flare for four weeks after each increase in dose. Prophylaxis for (TFR) is not recommended. Grade 1 TFR may be treated with NSAIDs (i.e. ibuprofen 400-600 mg orally every 4-6 hours as needed). TFR  $\geq$  Grade 2 may be treated with corticosteroids. Narcotic analgesics may be added as needed for pain control in subjects experiencing  $\geq$  Grade 2 tumor flare. If corticosteroids are used, the following dosage schedule is

recommended: prednisone 20 mg PO QD x 7 days followed by 10 mg PO QD x 7 days. (See Appendix D: Cairo Bishop Tumor Lysis Definition and Grading Criteria.)

### 5.3 Visit schedule and assessments

Screening Assessments and all on study scheduled visits and assessments are outlined in Section 10 Table of Study Assessments.

At treatment discontinuation, subjects will undergo off study evaluations per the Schedule of Assessments, Section 10. In addition, a safety assessment will be done approximately 28 days post the last dose of study drug. Follow-Up contact with the subjects should occur at a minimum of sixth months.

### 5.4 Drug Administration

#### 5.4.1 Dosing regimen

- Cycle -1: patients will receive thalidomide 50 mg PO daily on days 1-14 or lenalidomide PO on days 1-14, followed by no treatment days 15-28, as described previously in 5.1.
- Cycle 1 and subsequent cycles: Patients will receive thalidomide 50 mg (every **ODD** day on days 1-28 of a 28 day cycle) with lenalidomide (every **EVEN** day on days 1-28 of a 28 day cycle), as described previously. Each cycle will be 28 days in length.
- Cycle 1: Patients will also receive rituximab 375 mg/m^2 IV on Days 1, 8, 15 and 22 and then again on the same weekly x 4 schedule every 6th cycle through Cycle 19 (Cycle 7, 13, and 19), as described previously.

Patients unable to tolerate either thalidomide or lenalidomide will be removed from protocol. Patients unable to tolerate rituximab can continue on with protocol treatment without additional rituximab being administered.

Dosing of thalidomide and lenalidomide should be at bedtime in order to allow for the sedative effects of thalidomide to not cause daytime somnolence and to maintain regular dosing intervals. **Only enough lenalidomide for one cycle of therapy will be supplied to the patient each cycle.** At the start of any non-clinic visit treatment cycles subsequent to Cycle 24, one cycle of study drug will be shipped to the subject.

See Section 5.5 for allopurinol and oral hydration requirements as prophylaxis against tumor lysis syndrome (TLS).

Thalidomide and lenalidomide capsules should be swallowed whole, and should not be broken, chewed or opened.

If a dose of thalidomide or lenalidomide is missed, it should be taken as soon as possible on the same day. If it is missed for the entire day, it should not be made up.

Patients who take more than the prescribed dose of thalidomide or lenalidomide should be instructed to seek emergency medical care if needed and contact study staff immediately.

Subjects experiencing adverse events may need study treatment modifications (See section 5.6).

#### **5.4.2 Record of administration**

Accurate records will be kept of all study drug administration (including dispensing and dosing) will be made in the source documents. At all times, when dispensing study drug, research center personnel will review the instructions, printed on the packaging, with subjects. Subjects will be asked to maintain a diary to record the drug administration. Subjects will be asked to bring any unused study drug and empty study drug containers to the research center at their next visit. Research personnel will count and record the number of used and unused study drug capsules at each visit and reconcile with the patient diary. At the start of any non-clinic visit treatment cycles subsequent to Cycle 24, the packaging instructions will be reviewed with subjects by telephone call, and study drug and medication log will be shipped to the subject.

### **5.5 General Concomitant Medication and Supportive Care Guidelines**

#### **5.5.1 Recommended Concomitant Therapy**

Subjects should receive full supportive care, including transfusions of blood and blood products, antibiotics, and antiemetics when appropriate. Starting with Cycle -1 and while on study, subjects will receive prophylaxis against *Pneumocystis pneumonia* (with Bactrim DS thrice weekly or equivalent), varicella zoster (with valacyclovir 500 mg daily or equivalent), tumor lysis syndrome (with allopurinol and 8-10 eight ounce glasses of fluid daily), and thrombosis (with aspirin 81 mg daily).

Patients intolerant to or unable to take allopurinol beyond the first 2 cycles and can maintain adequate oral hydration are still eligible to continue to receive treatment on study. Patients who cannot take allopurinol for at least the first 2 cycles are to be removed from study.

Treating physicians must watch for signs of tumor lysis syndrome. It is recommended that all patients with signs of significant tumor lysis syndrome be hospitalized for monitoring, aggressive fluid management, and possible rasburicase.

#### **Hematopoietic Growth Factors**

Myeloid growth factors (G-CSF and pegfilgrastim only) may be used. GM-CSF may not be used given the theoretical impact it might have on CLL disease activity. Erythropoietic Stimulating Agents (ESAs; Aranesp, Procrit) may be used at the discretion of the treating physician and need to be recorded in the medication list.

### **Anticoagulation Considerations**

Patients already on aspirin or other anticoagulation should remain on the current anticoagulation dosing regimen they are on. If they are not on anticoagulation, then they should initiate prophylaxis with aspirin 81 mg or 325 mg daily on Day 1 of Cycle -1. Dose is at the discretion of the Investigator. Coumadin or low molecular weight heparin may be utilized in patients that are intolerant to ASA.

If prophylactic anti-coagulation is used, it should be held for platelet counts < 50,000/mm^3 and then restarted when platelet counts are above this level.

### **Tumor Lysis Syndrome Prophylaxis (allopurinol and hydration)**

Tumor lysis syndrome (TLS), characterized by hyperkalemia, hyperuricemia, and hyperphosphatemia resulting from the rapid release of potassium, uric acid, and phosphate, has been reported in CLL patients treated with lenalidomide necessitating TLS prophylaxis including allopurinol and oral hydration. The risk of TLS is highest during the first cycle of therapy and may be elevated when lenalidomide is re-started after treatment interruptions or when the lenalidomide dose is escalated.

If patients are intolerant or unable to take allopurinol beyond the first 2 cycles AND can maintain adequate hydration, it will be up to the discretion of the Investigator if patient can continue the treatment plan. Patients who cannot take allopurinol for at least the first 2 cycles are to be removed from study.

Allopurinol 300 mg daily beginning at least 3 days before the start of Cycle -1, continuing through any cycle of lenalidomide escalation and continuing, at least for one additional cycle post escalation as TLS prophylaxis is required for all subjects.

Subjects should be instructed to maintain adequate hydration and maintain urinary output as an additional measure to prevent TLS. To maintain fluid intake, subjects should be instructed to drink 8 to 10 eight ounce glasses of fluid each day for the first 14 days of Cycle -1 and Cycle 1 and any subsequent cycle of lenalidomide escalation.

Hydration levels should be adjusted according to age and clinical status, and lowered if the subject's cardiovascular status indicates the possibility of volume overload. Within the first 3 cycles of therapy, additional oral hydration should be considered concurrent with any dose escalation (or re-escalation, if permitted) of treatment, or when treatment is restarted after having been held for any reason.

Based on a patient's reaction and laboratory parameters, TLS prophylaxis may be continued or restarted as needed at the Investigator's discretion.

## **Treatment and Dose Modification for Tumor Lysis Syndrome**

All subjects meeting criteria of laboratory TLS or  $\geq$  Grade 1 TLS according to the Cairo-Bishop Definition of Tumor Lysis Syndrome (see Appendix D) should receive vigorous intravenous hydration and should be considered for rasburicase therapy as needed to reduce hyperuricemia, until correction of electrolyte abnormalities.

- In cases of laboratory TLS and Grade 1 TLS (see Appendix D: Cairo-Bishop Definition of Tumor Lysis Syndrome), lenalidomide and thalidomide will be continued at the same dose without interruption or dose reduction. TLS prophylaxis measures outlined in Section 5.5.1 should be continued or re-instituted.
- Subjects with  $\geq$  Grade 2 TLS (see Appendix D: Cairo-Bishop Definition of Tumor Lysis Syndrome) will be managed as follows in addition to intravenous hydration and consideration for rasburicase therapy (above).
  - Hold (interrupt) treatment.
  - First episode: restart lenalidomide and thalidomide at the current dose with appropriate TLS prophylaxis (Section 5.5.1) after resolution of electrolyte abnormalities to Grade 0.
  - Subsequent episodes: restart lenalidomide and thalidomide with appropriate TLS prophylaxis (Section 5.5.1) after resolution of electrolyte abnormalities to Grade 0. At physician discretion, the doses of lenalidomide and thalidomide may be restarted at the current dose or the dose of lenalidomide and/or thalidomide may be reduced by 1 dose level.
  - First or subsequent episodes: subjects should be closely monitored for signs of TLS after resuming treatment. To monitor for TLS, serum chemistry and uric acid tests should be performed at least every week following initiation of treatment for 4 consecutive weeks and on Day 3 or 4 following initiation of treatment. See Section 10, Schedule of Study Assessments, for additional specifics regarding serum chemistry and uric acid testing.

## **Tumor Flare Reaction**

Prophylaxis for (TFR) is not recommended. Grade 1 TFR may be treated with NSAIDs (i.e. ibuprofen 400-600 mg orally every 4-6 hours as needed). TFR  $\geq$  Grade 2 may be treated with corticosteroids. Narcotic analgesics may be added as needed for pain control in subjects experiencing  $\geq$  Grade 2 tumor flare. If corticosteroids are used, the following dosage schedule is recommended; prednisone 20 mg PO QD x 7

days followed by 10 mg PO QD x 7 days. Given the potential for tumor flares to occur at each escalation of lenalidomide dose, prednisone treatment may be repeated at each occurrence of tumor flare. Patients experiencing tumor flares should not have their dose of lenalidomide escalated the subsequent cycle.

Tumor flare occurring during a cycle when the dose of lenalidomide or thalidomide was escalated should be recorded as an adverse event and not as progressive disease (PD). For tumor flare occurring after the first 2 weeks of any cycle of lenalidomide escalation, it is up to the discretion of the physician to differentiate tumor flare from progression. It is expected that some degree of tumor flare reaction is likely until the patient is on the maximum dose of lenalidomide for more than four weeks. Because of this and the typically indolent nature of CLL, investigators are encouraged to continue escalating a subject's lenalidomide dose if safe and not to determine a patient as having progressive disease until after they have been on the maximum dose of lenalidomide for more than four weeks.

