≥ 60 ml/min	5 mg every EVEN day during Days 1 – 28 of each 28-day cycle**
≥ 30 and < 60 ml/min	5 mg every 2 nd EVEN day during Days 1 - 28 of each 28-day cycle**

\*\*For patients who receive lenalidomide during Cycle -1, the lenalidomide dose during Cycle -1 will be at the dose indicated above (5 mg every other day or 5 mg every 2nd EVEN day depending on baseline calculated creatinine clearance) taken daily on Days 1 – 14 of the 28-day cycle.

At investigator discretion, the lenalidomide dose may be gradually increased in a step-wise manner (in 5 mg increments) at the start of any subsequent 28-day treatment cycle beginning with the start of Cycle 2, if the patient tolerated the prior treatment cycle without requiring dose modifications, interruptions or delays due to toxicity. For patients who initiate therapy at a lenalidomide 5 mg every 2nd EVEN day starting dose, the first dose titration would be to lenalidomide 5 mg every EVEN day, and subsequent dose titrations would be permitted in 5 mg increments. The lenalidomide dose may only be increased at the start of a new cycle of therapy, may only be increased once every 28 days (or less frequently), and may only be increased if the prior treatment cycle was completed without requiring dose modifications, interruptions or delays due to toxicity. For patients who initiate treatment at lenalidomide 5 mg based on baseline calculated creatinine clearance  $\geq 60$ ml/min, the maximum allowable dose is lenalidomide 25 mg every EVEN day during Days 1-28 of a 28-day cycle. For patients who initiate treatment at lenalidomide 5 mg every 2nd EVEN day due to baseline calculated creatinine clearance  $\geq 30$ ml/min but  $< 60$ ml/min, the maximum allowable dose is lenalidomide 15 mg every EVEN day during Days 1-28 of a 28-day cycle.

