## 11. MEASUREMENT OF EFFECT

Baseline lesion assessments must occur within  $\leq 28$  days of study drug administration or as indicated in Section 10, Schedule of Study Assessments.

Efficacy assessments are scheduled to occur every four weeks. It should be noted that signs and symptoms of a tumor flare may appear similar to disease progression. Investigators should decide whether apparent increases in disease are indicative of a tumor flare or disease progression. If the increases in lymphadenopathy, tenderness, leukocytosis, or cytopenias occur within four weeks of a dose escalation, then it is possible the changes are indicative of a disease flare. If these changes begin more than four weeks after a dose increase, then the changes are likely disease progression. These are guidelines to help investigator in making their decision, but the decision regarding classifying their disease as progression or flare remains ultimately with the investigator.

Response and progression will be evaluated in this study using the International Workshop on CLL (IWCLL) update of the 1996 NCI-Working Group criteria for CLL [15].

11.1 **Complete response:** requires all of the following conditions to be met:

1. Absence of clonal lymphocytes in the peripheral blood by flow cytometry.
2. Blood counts above the following values:
  - a) neutrophil count  $> 1500/ \text{mm}^3$ , without the use of growth factors
  - b) hemoglobin  $> 11 \text{ gm/dL}$ , untransfused (men and women)
  - c) platelet count  $> 100,000/ \text{mm}^3$ , untransfused
3. Absence of lymphadenopathy on CT examination of the neck, chest, abdomen, and pelvis (lymph nodes  $< 1.5 \text{ cm}$  in diameter).
4. Absence of hepatomegaly or splenomegaly by CT examination
5. Absence of constitutional symptoms.
6. Bone marrow biopsy and aspirate demonstrating normal cellularity for the age of the patient and free of clonal CLL cells by conventional (not 4-color) flow cytometry and / or immunohistochemistry. If lymphoid nodules are present (formerly nPR), they should be assessed by immunohistochemistry to determine whether they are composed of CLL cells. If the lymphoid nodules are not CLL cells, then the patient will be considered a CR. If the lymphoid nodules are composed of CLL cells, then the patient will be categorized as a PR. If the bone marrow is found to be hypocellular, a repeat marrow biopsy should be performed after 4-6 weeks.

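### Section 5.5.1 discourages a progression call that Section 11 treats as likely, and no rule says how a deferred progression is dated for PFS

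*Combined protocol and SAP*

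**What the plan says.** Three places in the combined protocol and SAP deal with telling tumor flare from progression.

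- **Section 5.2** opens with "While no strict criteria can be established for this distinction" and then says that "rapid changes in clinical status that occur within four weeks of a dose escalation are likely to be tumor flares".
- **Section 11** uses the same four-week window. Within it, flare is possible. Beyond it, "If these changes begin more than four weeks after a dose increase, then the changes are likely disease progression". The section calls its text guidance and leaves the decision to the investigator.
- **Section 5.5.1 (Tumor Flare Reaction)** makes several statements. Flare in a cycle with a dose escalation is to be recorded as an adverse event rather than progression. On telling the two apart it then says: "For tumor flare occurring after the first 2 weeks of any cycle of lenalidomide escalation, it is up to the discretion of the physician". A patient with a flare should not be escalated in the following cycle. The closing sentence favors further escalation where this can be done safely. On progression, its advice to investigators is "not to determine a patient as having progressive disease until after they have been on the maximum dose of lenalidomide for more than four weeks".

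Escalation itself is optional: "At investigator discretion, the lenalidomide dose may be gradually increased in a step-wise manner" (Section 5.1). It proceeds by at most one step per 28 days, from Cycle 2. The cap is 25 mg, or 15 mg for patients who start with reduced creatinine clearance.

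Section 5.6 ends treatment at progression but not at flare. Section 11.7 ends PFS at the first sign of progression. Section 13.3 ends it at objective or symptomatic progression, and otherwise censors at last follow-up.

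**The concern.** Section 11 looks at the time since the last dose increase, whatever the dose level. The last sentence of Section 5.5.1 looks at the time on maximum dose. The two part company when a patient sits below the maximum for more than four weeks. The same nodal growth is then likely progression under one section and something not to be called under the other. The progression criteria in 11.3 contain no maximum-dose condition.

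No text says which section governs. Nor does any text say whether maximum dose is the protocol cap or the patient's own highest tolerated dose, or what date a progression carries if its call was deferred. In an open-label, single-arm trial with investigator-made calls, advice that only delays the call can only lengthen PFS. If the change is never reclassified, the patient may be censored instead of counted as an event.

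**Working it through.** **Inputs.** Cycles last 28 days, and Cycle -1 is followed directly by Cycle 1 (Section 5.1). PFS starts on the first treatment day, so Cycle -1 Day 1 is day 1. Day 1 of Cycle k (k ≥ 1) is then 28k + 1: Cycle 2 = 57, Cycle 3 = 85, Cycle 4 = 113, Cycle 5 = 141, Cycle 6 = 169, Cycle 7 = 197. The dose steps are those of Section 5.1 and Table 1 in Section 6.1. Maximum dose is read as the protocol cap, which is an assumption.

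**Fastest escalation.**
- Standard start: 10, 15, 20 and 25 mg on days 57, 85, 113 and 141. Four weeks at 25 mg end on day 141 + 27 = 168.
- Reduced clearance: 5 mg every EVEN day, then 10 and 15 mg, on days 57, 85 and 113. Four weeks at 15 mg end on day 113 + 27 = 140.

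On this path the patient is never more than four weeks past an increase from day 57 until the deferral ends. Sections 5.2 and 11 therefore also allow for flare, and the sections hardly conflict.

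**Paused escalation.** The dose goes to 10 mg on day 57, there is no Cycle 3 escalation, and nodes enlarge on day 86, which is 86 − 57 = 29 days after the increase. Section 11 says likely progression.

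| After day 86 | 15 / 20 / 25 mg on day | Section 5.5.1 discourages a call through | Days after day 86 |
|---|---|---|---|
| Escalation every cycle from Cycle 4 | 113 / 141 / 169 | 169 + 27 = 196 | 110 |
| Change called flare, Cycle 4 escalation blocked | 141 / 169 / 197 | 197 + 27 = 224 | 138 |

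The first row requires that the change is not recorded as flare. Day 86 is the onset. The next node examination scheduled in Section 10 is Cycle 3 Day 8 (day 92); counted from there the gaps are 196 − 92 = 104 and 224 − 92 = 132 days.

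**Weeks 3 and 4 of an escalation cycle.** One sentence of Section 5.5.1 covers the whole cycle: adverse event, not progression. The next leaves the distinction to the physician after week 2. For the same two weeks, Section 5.2 says flare is likely and Section 11 says it is possible.

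**Best response.** Section 13.1 counts responses from after Cycle 6, which ends on day 196. In the example, a Section 11 call ends treatment in Cycle 3, whereas a deferred call leaves the patient on treatment at or beyond that point.

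To see how sensitive the decision rule is, take the plan's design: continue with 7 or more of 11, succeed with 18 or more of 24. P(success) = Σ (x = 7 to 11) b(x; 11, p) × P(Bin(13, p) ≥ 18 − x). This gives 0.093 at p = 0.60 and 0.801 at p = 0.80, which agrees with the stated 10% level and 80% power. One patient is 1/24 = 4.2 points. The documents give no size for any shift in recorded response, so these are assumed:

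| Assumed shift (points) | P(success), 60% shifted up | P(success), 80% shifted down |
|---|---|---|
| 2 | 0.130 | 0.725 |
| 5 | 0.205 | 0.597 |
| 10 | 0.380 | 0.380 |

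The upward column stands for deferral that keeps later responders on treatment, the downward column for flares called progression. Neither is an estimate.

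**The case against.** The strongest reply is that nothing here binds. Section 5.2 disclaims strict criteria, Section 5.5.1 only encourages, and Section 11 leaves the call to the investigator, who may declare progression at any time. That stands, and it rules out several stronger readings.

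- A reader might infer three mutually incompatible rules. Sections 5.2 and 11 share one window and differ only in strength of wording; Section 5.5.1 is the outlier. Its two-week sentence can also be read as qualifying the sentence before it.
- A reader might infer that progression cannot be called before maximum dose, so that some patients can never progress. That turns advice into a prohibition. It also assumes the cap is meant; because escalation is advised only if safe, the patient's own highest dose is a possible reading, and it would end the deferral sooner.
- A reader might size the problem from the fastest schedule, for example with a change on day 60. That is three days after the Cycle 2 escalation, when every section allows for flare.
- A reader might infer a biased primary endpoint. At the fastest escalation the deferral ends before responses count, and a retained patient must still meet 11.1 or 11.2.

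The first-sign wording in 11.7 can also be read as back-dating a deferred progression, and flares are already recorded as adverse events with their duration (Section 7.3.2). Both points reduce the problem. But 13.3 words PFS differently, and neither section addresses a change first called flare. Investigator discretion does not resolve contradictory guidance; it makes a stated dating rule more useful.

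**Conclusion.** The concern holds in a limited form. Section 5.5.1 conflicts with Section 11 for patients below maximum dose and more than four weeks past the last increase, and it is inconsistent on its face for weeks 3 and 4 of an escalation cycle. Under the worked path the call is discouraged for 110 to 138 days from onset. That rests on paused escalation, on the cap as the meaning of maximum dose, and on an investigator who follows the advice. With steady escalation, or if first sign is applied as back-dating, the shift in PFS shrinks or disappears.

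The deferral pushes in one direction only, toward later progression. What it mainly affects is the date of PFS events. Best response is touched only through who is still on treatment when responses start to count, and the documents do not support a figure for that. This should be corrected, but it does not undermine the primary analysis.

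**What to change.** 1. Reconcile Sections 5.2, 5.5.1 and 11, say which governs, and define maximum dose. Which clinical rule to adopt is for the investigators and sponsor.
2. In Sections 11.7 and 13.3, add one dating rule for the analysis. When a change meeting 11.3 was first called flare, did not resolve and was later judged progression, the progression date is the first assessment at which 11.3 was met. This agrees with the first-sign wording.
3. Define unresolved in advance, and record each flare call with its start and resolution dates.
4. Report one PFS sensitivity analysis that counts every unresolved 11.3 event at its first occurrence, whatever it was called at the time.

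The cost is some wording, one CRF item and one extra analysis. PFS may look slightly shorter. The primary endpoint, sample size and stopping boundaries do not change.
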